4.2.2 SECONDARY PERFORMANCE ENDPOINTS

- Improvement in appearance of surgical scars at 1 and 2 months post-treatment as evaluated by independent blinded reviewer using the General Aesthetic Improvement Scale (GAIS) and Manchester Scar Scale (MSS).
- Assessment of surgical scars at 3 and 10 months post-treatment as evaluated by independent blinded reviewer using the Patient and Observer Scar Assessment Scale (POSAS).
- Assessment of surgical scars at 3 and 10 months post-treatment as evaluated by the subject using the Patient and Observer Scar Assessment Scale (POSAS).
- Subjects' assessment of satisfaction (5-point Likert Scale) with the treatment at 3 and 10 months post-treatment.

Safety endpoints:

- Subject's assessment of discomfort and pain after treatment as measured by a 10 cm visual analog scale (VAS).
- Subjects experiencing a treatment-related adverse event (AE) by 10 months post-treatment.

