5.5.2 HANDLING OF PARTICIPANT WITHDRAWALS OR TERMINATION

Every effort will be made to continue follow-up of withdrawn or terminated subjects or subjects who discontinue the intervention but remain in the study for follow-up, especially for safety and performance study endpoints. Every effort will be made to conduct an exit visit (final study visit, see section 7.3.5) to withdrawn patients, and to undertake protocol-specified safety follow-up procedures to capture AEs, serious adverse events (SAEs) and device deficiencies.

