The investigator will examine the treated areas and report immediate and short term response (30 minutes post-treatment) (pain during treatment, hemorrhage, burn, erythema, edema, purpura) using a 5-point scale: 1=none; 2=trace; 3=moderate; 4=marked; 5=severe.

The assessment of discomfort/pain based on the subject's completion of the 10 cm VAS should also be documented immediately after each treatment.

The normal response to these treatments is transient erythema and edema. If any other side effects occur, as indicated in the protocol, they must be recorded.

Subjects will be discharged from the clinic and will be instructed to return in 2-3 days in order to be examined for adverse events.

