7.3.3 FOLLOW-UP

Visit 3, Day 0+2 days

Subjects will be examined 2-3 days after treatment for the occurrence of adverse events. Vital signs and any changes in concomitant medication will be recorded. Subjects will be discharged from the clinic and will be instructed to return for the Month 1 assessment and treatment.

Visit 4, Month 1 (\pm 7 days)

Subjects will return to the clinic one month after the first treatment. Adverse events, vital signs and any changes to concomitant medications will be recorded.

Subjects will receive treatment as described in section 7.3.1. Following treatment, the investigator will examine the treated area and report immediate and short term response. Subjects will complete the 10 cm discomfort/pain VAS immediately after treatment.

Subjects will be discharged from the clinic and will be instructed to return in 2-3 days in order to be examined for adverse events.

Visit 5, Month 1+2 days

Subjects will be examined 2-3 days after treatment for the occurrence of adverse events. Vital signs and any changes in concomitant medication will be recorded. Subjects will be discharged from the clinic and will be instructed to return for the Month 2 assessment and treatment.

Visit 6, Month 2 (\pm 7 days)

Subjects will return to the clinic one month after the second treatment. Adverse events, vital signs and any changes to concomitant medications will be recorded.

Subjects will receive treatment as described in section 7.3.1. Following treatment, the investigator will examine the treated area and report immediate and short term response. Subjects will complete the 10 cm discomfort/pain VAS immediately after treatment.

Subjects will be discharged from the clinic and will be instructed to return in 2-3 days in order to be examined for adverse events.

Visit 7, Month 2+2 days

Subjects will be examined 2-3 days after treatment for the occurrence of adverse events. Vital signs and any changes in concomitant medication will be recorded. Subjects will be discharged from the clinic and will be instructed to return for the Month 3 assessment.

Visit 8, Month 3 (\pm 7 days)

Subjects will return to the clinic one month after the third treatment. Adverse events, vital signs and any changes to concomitant medications will be recorded.

Photographs of the treated area will be taken as described in section 7.3.1. Subjects will be discharged from the clinic and will be instructed to return for the Month 4 assessment.

Visit 9, Month 4 (\pm 7 days)

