10.4.2 ANALYSIS OF THE PRIMARY PERFORMANCE ENDPOINT(S)

The following will be considered for the analysis primary performance endpoint:

Summary table for differences of baseline, 3-month and 10-month post treatment General Aesthetic Improvement Scale (GAIS) and Manchester Scar Scale (MSS) scores will be displayed as mean difference, standard deviation and standard error. The General Aesthetic Improvement Scale (GAIS) scores is a 5-point scale improvement assessment chart while Manchester Scar Scale (MSS) is two scales whose scores are combined - an overall VAS and seven scar parameters.

Bar, pie charts or graphs indicating scores will also be used to analyse performance, where applicable.

All statistical tests will be two-sided. The level of statistical significance for effectiveness analyses is 5% ($\alpha = 0.05$) for all tests of differences. Where appropriate, Paired t-test and/or Wilcoxon Signed-Ranks Test for Matched Pairs will be used to compare the evaluations of General Aesthetic Improvement Scale (GAIS) scores and Manchester Scar Scale (MSS) scores at 3 and 10 months against baseline. Analysis of Covariance (ANCOVA) may also be used where appropriate.

The Paired t-test and/or Wilcoxon Signed-Ranks Test for Matched Pairs will enable us to accept or reject the null hypotheses. Rejection of null hypotheses will establish that:

- The two-sided 95% confidence interval for the difference between the means excludes zero.
- The two means are statistically significantly different at the 5% level ($P < 0.05$) two-sided.

Upon rejection of null hypotheses, further statistical test tools such as Confidence Interval and/or t-test will be used to test expected primary performance endpoint; that is alternative hypothesis that $H_a \geq 1$. This will be used to determine if the study meets the primary performance endpoint.

General Aesthetic Improvement Scale (GAIS) scores and Manchester Scar Scale (MSS) scores of all subjects who received at least one treatment of Venus Viva™ system for the treatment of surgical scars following breast augmentation, abdominoplasty or face lift and for whom at least one valid post-baseline GAIS and MSS assessment were obtained will be analysed for the primary endpoint. Multiple imputation method or modelling of available data may be used for missing data as appropriate.

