10.4.4 SAFETY ANALYSES

The safety analysis will be done by analyzing spontaneous reports of adverse events (AE), subjects' completed 10 cm discomfort/pain VAS and a response questionnaire as well as analysis of immediate and short term response reports by the principal investigator from his/her observation/examination of the treated area. Appropriate Medical Dictionary for Regulatory Activities (MedDRA) code will be used to describe all spontaneously reported or other study related adverse events.

Summaries of spontaneously reported or other study related adverse events will be presented as:

- Number (%) of subjects with any AE,
- Number (%) of subjects with any serious adverse events (SAE),
- Number (%) of subjects permanently withdrawn from treatment due to AE

Summaries of analysis of immediate and short term response reports by the principal investigator examination will be displayed on a bar or pie chart as;

- the overall frequency of subjects with each event (pain during treatment, hemorrhage, burn, erythema, edema, purpura)
- Frequency of subjects with specific severity/intensity for each event using a 5 points scale: 1=none; 2=trace; 3=moderate; 4=marked; 5=severe
- The overall percentage or proportion of subject observed with marked or severe intensity of any event will be calculated and compared to those with none, trace or moderate severity/intensity with the aid of a bar or pie chart.

The following will be considered for the analysis of 10 cm discomfort/pain VAS scores safety data:

Summary table for differences of baseline post-treatment (Visit 2) and Visit 6 post-treatment 10 cm discomfort/pain VAS scores will be displayed as mean difference, standard deviation and standard error. The 10 cm discomfort/pain VAS is a 11-level (0 to 10) ordinal scale tool for assessing pain.

Bar, pie charts or graphs indicating scores, percentages or proportions of subjects with Visit 6 and baseline (Visit 2) post-treatments VAS scores difference that is < 1 and > 1 will be used to analyse subjects' tolerability of this treatment.

All statistical tests will be two-sided. The level of statistical significance for effectiveness analyses is 5% ($\alpha = 0.05$) for all tests of differences. Where appropriate, Paired t-test and/or Wilcoxon Signed-Ranks Test

for Matched Pairs will be used to compare the difference between Visit 2 and Visit 6 post treatment VAS scores.

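### The pain VAS is analysed only as Visit 6 minus Visit 2, so treated subjects without a third session drop out of every VAS result, with a bias that could go either way

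*Combined protocol and SAP*

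**What the plan says.** The safety endpoint in section 4.2.2 is discomfort and pain after treatment on a 10 cm VAS. It is not restricted to subjects who complete the course. Section 7.3.2 says that "completion of the 10 cm VAS should also be documented immediately after each treatment". Section 7.3.3 repeats the instruction for the second and third treatments (Visits 4 and 6): "Subjects will complete the 10 cm discomfort/pain VAS immediately after treatment". Each fully treated subject therefore has three scores.

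The analysis uses two of them, and only as a difference:

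- **Hypothesis (10.2):** Visit 6 against Visit 2, with an expected mean difference of at most 1.
- **Table (10.4.4):** "Summary table for differences of baseline post-treatment (Visit 2) and Visit 6 post-treatment 10 cm discomfort/pain VAS scores".
- **Chart (10.4.4):** displays of the Visit 6 and Visit 2 "VAS scores difference that is < 1 and > 1 will be used to analyse subjects' tolerability of this treatment".
- **Test (10.4.4):** a paired t-test and/or the Wilcoxon test "for Matched Pairs will be used to compare the difference between Visit 2 and Visit 6 post treatment VAS scores", followed by a test of the limit of 1.

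Section 10.3 sets the population for safety as subjects with at least one treatment and at least one valid post-baseline evaluation. Section 5.5.2 foresees "subjects who discontinue the intervention but remain in the study for follow-up". For the performance endpoints, sections 10.4.2 and 10.4.3 add that "Multiple imputation method or modelling of available data may be used for missing data as appropriate". Section 10.4.4 has no such sentence.

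**The concern.** A Visit 6 score exists only if the third treatment is given. Someone who stops after the first or second session but stays in follow-up can belong to the section 10.3 set and still contribute nothing to the VAS estimate, test or chart. The VAS results then describe a smaller group than the declared safety population, and no denominator is stated to show it.

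The loss may not be neutral. Sections 2.3.1 and 8.2.3 list significant post-treatment pain as a known risk, section 5.5.1 lets the investigator end participation for an adverse event, and a painful session is a plausible reason not to return. Two things are at stake: whether the tested change applies to everyone treated, and whether the chart named as the tolerability analysis shows the experience of those who stopped.

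**Working it through.** **Plan's own figure.** There is none for the VAS: no mean, SD, power or sample size. The only sample size, in section 10.5, is for GAIS. It reproduces with the 90% power quantile ((1.96 + 1.2816)² = 10.51, rounded to 11; 11 × 1.3 = 14.3, rounded to 15) and plays no part here.

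**Step 1: how many pairs could be lost.** Maximum enrolment is 50 + 25 = 75. If a fraction d has no third treatment, pairs = 75 × (1 − d). The values of d are assumed.

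| d | Pairs | Omitted |
|---|---|---|
| 10% | 67.5 | 7.5 |
| 20% | 60 | 15 |
| 30% | 52.5 | 22.5 |

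The 30% row is a ceiling only. The section 10.5 allowance covers loss for any reason over treatment and follow-up, whereas Visit 6 falls at Month 2.

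**Step 2: what the chart leaves open.** Let p be the share of completers with a difference above 1. With nothing assumed about the stoppers, the share among all treated lies between (1 − d)p and (1 − d)p + d. For an assumed p of 10%, that is 9% to 19% at d = 10%, 8% to 28% at d = 20%, and 7% to 37% at d = 30%.

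**Step 3: direction of bias in the mean change.** Write Y2, Y4 and Y6 for the three scores and D = Y6 − Y2. Assume a common SD σ and a common correlation ρ between visits.

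- *Stopping on Visit 2 pain.* Cov(D, Y2) = (ρ − 1)σ², which is negative. Each point of Y2 above average lowers the expected change by 1 − ρ, or 0.3 to 0.5 for ρ of 0.5 to 0.7. Losing high scorers moves the completer mean change up, against the device.
- *Stopping on Visit 4 level.* Cov(D, Y4) = ρσ² − ρσ² = 0, so there is no shift.
- *Stopping on the rise from Visit 2 to Visit 4.* Cov(D, Y4 − Y2) = (ρ − ρ − ρ + 1)σ² = (1 − ρ)σ², which is positive. Losing those with a rise moves the completer mean change down, in the device's favour. This route cannot apply to anyone who stops after the first treatment.

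Simulations agree. They assume mean VAS 4, SD 1.5 to 2.5, ρ 0.5 to 0.7, a true rise of 0 or 1, and a stopping chance of 5% plus 6 points per VAS point above 4. Stopping on Visit 2 pain (9% to 11% stop) raised the completer mean change by 0.02 to 0.10 and the share above 1 by about 1 percentage point. Stopping on Visit 4 level moved it by about zero. Stopping on the Visit 2 to Visit 4 rise, under a steeper stopping rule, gave 0.87 against a true 1.01. A repeated-measures model on Visits 2, 4 and 6 returned 1.01 to 1.02 in all three cases.

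**Step 4: what a change score hides.** A second simulation takes mean 4, the same SDs and correlations and no true change, and removes the subjects with the highest pain at Visits 2 or 4. With 30% removed:

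- The completers' mean change is 0.12 to 0.33, well inside the limit of 1.
- Their Visit 6 mean is 3.17 to 3.60. The mean over all treated is 4.25 to 4.67 when each stopper's worst score is counted.
- Visit 2 scores of 7 or more, held by about 2% to 12% of all treated, are absent from the paired set. The same is true with 20% removed.

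The contrast can meet its limit while the most painful experiences are out of view.

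**The case against.** The strongest reply is that early stoppers are not lost from the safety report. Section 10.4.4 tabulates permanent withdrawals from treatment due to adverse events and grades investigator-reported pain during treatment. Section 10.4.1 shows missing counts where relevant, section 10.4.5 counts missing endpoint data by reason, including discontinuation of the intervention, and section 10.4.10 lists individual data by time point. All of this stands, so the point is confined to the VAS. None of these outputs puts a stopper's VAS score into an estimate, test or chart.

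A reader might infer that losing the stoppers makes the device look better tolerated than it was. The documents do not support that for the mean change. The natural mechanism, stopping because a session hurt, acts through pain level, and Step 3 shows that it pushes the completer change up or leaves it alone. A favourable bias needs stopping driven by a worsening between Visits 2 and 4. Letting the Visit 6 rise itself drive earlier stopping would assume the answer, since those subjects never experienced it.

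A reader might also take the 30% allowance as the likely loss. It is an all-cause figure for the whole study, not a rate of pain-related stopping before Month 2.

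Finally, counting everyone who stops for pain as exceeding a change limit would turn a change measure into a composite. That objection is fair, and the fix below avoids it.

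**Conclusion.** The point holds for the VAS analyses. They are restricted to subjects treated at Visit 6, which does not match the at-least-one-treatment basis of section 10.3, and the Visit 4 score is collected but unused. If stopping depends on pain, the completer-only change may be biased in either direction. Under the assumptions above the shifts were small, from +0.10 to about −0.14 (0.87 − 1.01). The clearer loss is of pain level among those who stopped. The actual size cannot be derived, because the documents give no VAS mean, SD, between-visit correlation or pain-related stopping rate. The directions in Step 3 rest on equal variances and equal correlations between visits. This is a cheap improvement, not a flaw that invalidates the safety assessment.

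**What to change.** In section 10.4.4:

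1. Estimate the Visit 6 minus Visit 2 change from a repeated-measures mixed model using every VAS score at Visits 2, 4 and 6 from all treated subjects. State its assumption that stopping depends only on scores already recorded.
2. Summarise the VAS level after each treatment, and the worst score per subject, in all treated subjects.
3. In the tolerability chart, use all treated subjects as the denominator. Show those with no third treatment as separate categories by reason (pain or adverse event; other), without counting them as failures.

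Section 10.3 also asks for a valid post-baseline performance evaluation. The VAS text should say that this does not apply to it, in line with the Protocol Summary, which analyses all subjects with at least one treatment.

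The cost is SAP wording and a little more analysis on data already collected. Section 10.1 allows such a revision before database lock. The reported tolerability share may look slightly less favourable.

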2.3 POTENTIAL RISKS AND BENEFITS

2.3.1 KNOWN POTENTIAL RISKS

The potential risks for adverse events of the treatment procedure include but are not limited to discomfort or significant pain post-treatment, excessive skin redness (erythema) and/or swelling (edema), in-grown hairs, damage to natural skin texture (crust, blister, burn), change of pigmentation (hyper- and hypo-pigmentation) and scarring. Treatment of hair-bearing areas in male patients may result in some damage to the follicles and subsequent loss of hair. Avoid the beard area and other hair-growing zones if the patient does not wish to experience hair growth reduction.

Further information about residual risks associated with the device and with participation in the clinical investigation are reported in the device User Manual.

Residual risks will be mitigated as follows:

- Selection of Investigator with experience in the therapeutic area of the clinical investigation
- Investigator will undergo training prior to patients' enrollment
- For the first procedure of each site, an experienced person with the use of the device, representing the sponsor, will attend.
- Patients will be rigorously screened prior to their enrollment
- Patients will be rigorously followed over the course of the study

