 - **Null Hypothesis ($H_0: \mu_d = \mu_{post} - \mu_{pre} = 0$)** – There is no improvement of surgical scars at 3 and 10 months post-treatment review compared to baseline.
Alternative Hypothesis ($H_a: \mu_d = \mu_{post} - \mu_{pre} \neq 0$) – There is improvement of surgical scars at 3 and 10 months post-treatment review compared to baseline. The improvement of surgical scars will be defined using Patient and Observer Scar Assessment Scale (POSAS) scores evaluated by the subject.
 - **Null Hypothesis ($H_0: \mu_d = \mu_{post} - \mu_{pre} = 0$)** – There is no satisfaction with treatment as documented on a 5-point Likert scale at 3 and 10 months compared to baseline.
Alternative Hypothesis ($H_a: \mu_d = \mu_{post} - \mu_{pre} \neq 0$) – There is satisfaction with treatment as documented on a 5-point Likert scale at 3 and 10 months compared to baseline. The satisfaction with treatment will be defined by 5-point Likert scale at 3 and 10 months compared to baseline as assessed by the subjects.
- Safety Endpoint:
 - **Null Hypothesis ($H_0: \mu_d = \mu_{post} - \mu_{pre} = 0$)** – There is no difference in subjects' 10 cm discomfort/pain VAS score experienced after at Visit 6 treatment and that of baseline treatment (Visit 2).
Alternative Hypothesis ($H_a: \mu_d = \mu_{post} - \mu_{pre} \neq 0$) – There is a difference in subjects' 10 cm discomfort/pain VAS score experienced after at Visit 6 treatment and that of baseline treatment (Visit 2). Expected mean difference is maximum VAS score ≤ 1 .

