The Paired t-test and/or Wilcoxon Signed-Ranks Test for Matched Pairs will enable us to accept or reject the null hypotheses. Rejection of null hypotheses will establish that:

- The two-sided 95% confidence interval for the difference between the means excludes zero.
- The two means are statistically significantly different at the 5% level ($P < 0.05$) two-sided.

Upon rejection of null hypotheses, further statistical test tools such as Confidence Interval and/or t-test will be used to test expected safety endpoint; that is alternative hypothesis, $H_a \leq 1$.

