10.4.6 BASELINE DESCRIPTIVE STATISTICS

Subjects baseline scores of all endpoints (GAIS, MSS and POSAS) will be compared using descriptive statistics such as mean score, standard deviation, standard error, range and graphical presentations.

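### The pain endpoint is a level, but every VAS analysis that section 10.4.4 names uses the Visit 2 to Visit 6 difference, so none shows how much pain subjects reported

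*Combined protocol and SAP*

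**What the plan says.** - **Endpoint.** Section 4.2.2 lists as a safety endpoint the subject's "assessment of discomfort and pain after treatment as measured by a 10 cm visual analog scale (VAS"). Nothing in that definition refers to a change between sessions.
- **Collection.** Sections 7.3.2 and 7.3.3 have the subject complete the VAS straight after each treatment, at Visits 2, 4 and 6.
- **Hypothesis.** Section 10.2 tests for a difference in "VAS score experienced after at Visit 6 treatment and that of baseline treatment (Visit 2"), with an expected mean difference of at most 1.
- **Table.** Section 10.4.4: "Summary table for differences of baseline post-treatment (Visit 2) and Visit 6 post-treatment 10 cm discomfort/pain VAS scores will be displayed as mean difference", with its standard deviation and standard error.
- **Tolerability display.** Section 10.4.4 groups subjects by Visit 6 and Visit 2 "post-treatments VAS scores difference that is < 1 and > 1 will be used to analyse" their tolerability of the treatment.
- **Tests.** Section 10.4.4 names a paired t-test and/or Wilcoxon signed-rank test of Visit 2 against Visit 6. If the null is rejected, a confidence interval and/or t-test "will be used to test expected safety endpoint; that is alternative hypothesis" of a difference of 1 or less.
- **Scale.** Section 10.4.4 states that the "VAS is a 11-level (0 to 10) ordinal scale tool for assessing pain".

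**The concern.** The endpoint asks how much the treatment hurt. The named analyses ask whether the third session hurt more or less than the first. These are different quantities, and the second does not contain the first.

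Section 2.3.1 lists "discomfort or significant pain post-treatment" among the known risks, so a reader of the report will want the level. A report that delivered exactly the named VAS outputs could say that most subjects had a difference below 1 without showing whether pain was low or high at both sessions. If pain were severe and unchanged, none of those outputs would show it.

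**Working it through.** The plan states no figure to reproduce here. The check is to compare what is measured with what is analysed, and then see what the named outputs can distinguish.

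**1. Where each VAS score is used**

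| Score | Collected (7.3.2, 7.3.3) | Difference table, split and tests (10.2, 10.4.4) | Named summary of the score itself |
|---|---|---|---|
| Visit 2 | yes | yes, as half of the difference | none |
| Visit 4 | yes | no | none |
| Visit 6 | yes | yes, as half of the difference | none |

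**2. Two subjects under the tolerability split**

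Difference = Visit 6 score minus Visit 2 score.

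- Subject A scores 9 and 9: 9 − 9 = 0, in the below-1 group.
- Subject B scores 0 and 2: 2 − 0 = 2, in the above-1 group.

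A reports near-maximal pain twice and lands on the favourable side. B reports little pain and lands on the other side. Section 10.4.4 does not say whether the split is on a signed or an absolute difference, but both results are the same either way (|0| = 0, |2| = 2).

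**3. The boundary**

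The split names below 1 and above 1, so a difference of exactly 1 is in neither group. On the 11-level scale that the plan describes, a one-step difference is an ordinary result. Section 10.2 and the end of section 10.4.4 put the bound for the mean difference at 1 or less, so the split does not match the plan's own criterion.

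**4. Same differences, three pain levels (assumed data)**

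Take 15 subjects whose differences are −2 (one subject), −1 (three), 0 (seven), +1 (three) and +2 (one). Give all of them a Visit 2 score of 2, then 5, then 8.

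- Mean difference: (−2 − 3 + 0 + 3 + 2) / 15 = 0.
- SD: sum of squares 4 + 3 + 0 + 3 + 4 = 14; √(14/14) = 1.0.
- SE: 1.0/√15 = 0.26.
- Paired t: 0/0.26 = 0, p = 1.0. The null is not rejected, so the follow-up test of 1 or less is not reached.
- Signed split: 1 + 3 + 7 = 11 below 1, 1 above 1, 3 in neither group.

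| Visit 2 score | Mean at Visit 2 | Mean at Visit 6 | Mean difference (SD, SE) | Below 1 / above 1 / neither | p |
|---|---|---|---|---|---|
| 2 | 2.0 | 2.0 | 0.0 (1.0, 0.26) | 11 / 1 / 3 | 1.0 |
| 5 | 5.0 | 5.0 | 0.0 (1.0, 0.26) | 11 / 1 / 3 | 1.0 |
| 8 | 8.0 | 8.0 | 0.0 (1.0, 0.26) | 11 / 1 / 3 | 1.0 |

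The difference table, split and test are identical in all three rows, while mean pain runs from 2 to 8.

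**5. Does another section supply the level?**

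- Section 10.4.1 sets which statistics a summary table shows, not which tables are made.
- Section 10.4.6 says "Subjects baseline scores of all endpoints (GAIS, MSS and POSAS) will be compared using descriptive statistics"; the VAS is not among them.
- Section 10.4.10 promises a listing of individual values, which is not a summary.
- The investigator's 5-point grade in section 10.4.4 covers pain during treatment and is not the subject's rating afterwards.
- For satisfaction, also subject-reported, section 10.4.3 names both the scores at each visit and their difference. The VAS gets only the difference.

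**The case against.** The best defence is that section 10.4.4 is not exclusive. It opens by committing to analyse the VAS that subjects complete, without limiting visits, and it introduces its list as things to be considered. Its chart sentence mentions scores, and its test is described as comparing two means, so the Visit 2 and Visit 6 means will be to hand. Treatment pain is also summarised by severity through the investigator's grade. All of this is true, and it limits the point to what the plan names. It does not remove the point: each VAS item actually specified is a difference, the chart sentence is tied to that difference, and no display of the means is promised.

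A reader might also infer more than the documents support:

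- **That pain data are lost, or Visit 4 discarded.** Section 10.4.10 lists every value by measure and time point.
- **That missing VAS scores go unreported.** Section 10.4.5 counts missing data for each endpoint assessment, by reason. Imputing pain for a session that was never given would make little sense.
- **That a known share of high-pain subjects would be labelled tolerant.** Counting possible score pairs gives no such figure. Of the 16 pairs with both scores 7 or more (an assumed cut), 10 are below 1 on a signed difference but only 4 on an absolute one, and possible pairs are not expected frequencies.
- **That changes in device settings between sessions invalidate the comparison.** Section 7.3.1 allows settings to be adjusted, but the natural reading is tolerability of the regimen as delivered.

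**Conclusion.** The point holds, and it is minor. The tolerability rule as written measures change where the endpoint is a level. It also leaves a difference of exactly 1 unclassified, against the bound used elsewhere in the plan, and it makes no use of Visit 4. This goes beyond missing detail, because a stated rule uses the wrong quantity and its boundary is inconsistent.

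The conclusion rests on the text of sections 4.2.2, 10.2 and 10.4.4 and on the arithmetic of differences. The 15-subject example uses assumed data and shows only what the named outputs cannot distinguish; it does not predict how much pain subjects will report. No primary endpoint, sample size or stated stopping rule depends on this analysis, and adverse events and investigator-graded responses, including burns, are summarised separately.

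**What to change.** In section 10.4.4:

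1. Make the main tolerability display a summary of the VAS score itself at Visits 2, 4 and 6: n, mean, SD, median, range and number missing, in the format that section 10.4.1 already sets.
2. Keep the Visit 6 minus Visit 2 difference and its test as supportive, and state that the difference is signed.
3. Write the split as 1 or less versus more than 1, to match section 10.2 and the follow-up test in section 10.4.4.

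The cost is one table and a one-line edit to the split. The scores are already collected after every session, so no new visits, CRF fields or subjects are needed.
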